Anti-RNP	Anti-Ribonucleoprotein
Anti-SSA	Anti-Sjögren's-syndrome A
Anti-SSB	Anti-Sjögren's-syndrome B
AST	Aspartate aminotransferase
ATC	Anatomical Therapeutic Class
AZA	Azathioprine
BICLA	British Isles Lupus Assessment Group-based Composite Lupus Assessment
BILAG	British Isles Lupus Assessment Group
BMI	Body Mass Index
CI	Confidence Interval
CLASI	Cutaneous Lupus Erythematosus Disease Area and Severity Index
CMV	Cytomegalovirus
CPK	Creatine PhosphoKinase
CRO	Contract Research Organization
CRP	C-Reactive Protein
CS	Clinically Significant
CS	Corticosteroid
CVS	Cardio Vascular System
DNA	Deoxyribonucleic acid
dsDNA	Double-stranded DNA
EBV	Epstein Barr Virus
ECG	Electrocardiogram
eCRF	Electronic Case Report Form
FACIT	Functional Assessment of Chronic Illness Therapy

Statistical Analysis Plan

Study Name: IFN-K-002

SAP version & date: v4, 18/Jun/2018

FAS	Full Analysis Set
FDA	Food and Drug Administration
FU	Follow-Up
GMT	Geometric Mean Titer
HIA	Hemagglutination Inhibition Assay
HCQ	Hydroxychloroquine
HCV	Hepatitis C Virus
HIV	Human Immunodeficiency Virus
HPV	Human Papillomavirus
HSV	Herpes Simplex Virus
hIFN- α	Human interferon α
ICH	International Conference on Harmonization
iDSMB	Independent Data and Safety Monitoring Board
IFN	Interferon
IFN-K	Interferon α -kinoid
IM	Intramuscular
INR	International Normalized Ratio
ITT	Intention-to-treat
IWRS	Interactive Web Response System
KLH	Keyhole Limpet Hemocyanin
LLDAS	Lupus Low Disease Activity State
Mcg	micrograms
MCID	Minimum Clinically Important Difference
MCS	Mental Component Summary
MedDRA	Medical Dictionary for Regulatory Activities
mL	milliliter
mm	millimeter
MMF	Mycophenolate mofetil
MTX	Methotrexate
NCS	Not Clinically Significant
PCS	Physical Component Summary
PGA	Physician Global Assessment
PP	Per Protocol
PT	Preferred Term

Statistical Analysis Plan

Study Name: IFN-K-002

SAP version & date: v4, 18/Jun/2018

PT	Prothrombin time
PTT	Partial Thromboplastin Time
Q1	First Quartile
Q3	Third Quartile
RBC	Red Blood Cell
RT qPCR	Reverse Transcription quantitative Polymerase Chain Reaction
SAF	Safety Population
SAE	Serious Adverse Event
SAP	Statistical Analysis Plan
SAS®	Statistical Analysis System
SELENA	Safety of Estrogen in Lupus Erythematosus National Assessment
SF-36	Short Form-36
SJC	Swollen Joint Count
SLE	Systemic Lupus Erythematosus
SLEDAI	Systemic Lupus Erythematosus Disease Activity Index-2000
SLICC/ACR-DI	Systemic Lupus International Collaborating Clinics/American College of
SOC	System Organ Class
SRI	SLE Responder Index
TEAE	Treatment Emergent Adverse Event
TESAE	Treatment Emergent Serious Adverse Event
VAS	Visual Analog Scale
VZV	Varicella Zoster Virus
WBC	White Blood Cell
WHO	World Health Organization

Statistical Analysis Plan

Study Name: IFN-K-002

SAP version & date: v4, 18/Jun/2018

1 Introduction

This document is the statistical analysis plan (SAP) for the IFN-K-002 study. Please note that this SAP applies only for the main visit up to week 36 (visit 12). The purpose of this SAP is to provide a comprehensive and detailed description of the statistical analyses that will be carried out to assess the efficacy (biological and clinical) and safety of the study treatment, as outlined in the study protocol version 6, dated 11 Apr 2016. The SAP pre-specifies the statistical approaches to be used and is validated prior to the study database lock and the unblinding of the randomization schedule, to ensure the credibility of the study findings.

This SAP covers the analysis of all data until Week 36. The analysis of the extended follow-up data will be detailed in a separate SAP according to protocol.

2 Highlights from study protocol

2.1 Background/Rationale

Full details of the background and rationale for the study are provided in Section 5 of the protocol version 6.0.

2.2 Study Objectives

2.2.1 Primary objective(s)

The primary objective of this study is to evaluate the neutralization of the IFN gene signature following treatment with IFN-K, as measured by the change from baseline of the expression of IFN-induced genes **and** to evaluate the efficacy of treatment with IFN-K using the British Isles Lupus Assessment Group (BILAG)-based Composite Lupus Assessment (BICLA) response criteria. The study will be considered as positive if a statistically significant better effect of IFN-K compared to placebo is observed on the neutralization of the IFN gene signature and if at least a trend favoring IFN-K is observed on the BICLA response.

2.2.2 Secondary objectives

The secondary objectives of this study are:

- To evaluate the efficacy of treatment with IFN-K using:
 - The SLE Responder Index [(SRI)-4 and above]
 - The SLE Disease Activity Index-2000 index (SLEDAI-2K)
 - The BILAG-2004 index
 - The Safety of Estrogen in Lupus Erythematosus National Assessment-SLEDAI (SELENA-SLEDAI) Flare index
 - The Systemic Lupus International Collaborating Clinics/American College of Rheumatology Damage Index for Systemic Lupus Erythematosus (SLICC/ACR-DI)
 - The Cutaneous Lupus Erythematosus Disease Area and Severity Index (CLASI) in patients with cutaneous lesions at baseline
- To evaluate the immune response induced by IFN-K:

Statistical Analysis Plan

Study Name: IFN-K-002

SAP version & date: v4, 18/Jun/2018

- Anti-IFN α antibody response
- Anti-IFN α antibody neutralizing capacities
- Anti-KLH antibody response
- To assess the safety of IFN-K emulsified with ISA 51 VG

2.2.3 Exploratory objectives

The exploratory objectives of this study are:

- To assess disease activity using:
 - The Physician Global Assessment (PGA) score
 - The 28-Tender and Swollen joint counts
 - A Joint Pain Visual Analog Scale (VAS)
 - The flare description
 - The changes in Lupus therapy
- To assess quality-of-life using:
 - The Short Form-36 (SF-36) questionnaire
 - The Functional Assessment of Chronic Illness Therapy (FACIT) fatigue score.
- To assess biological parameters:
 - Levels of lupus-related serum auto-antibodies and biomarkers
 - Neutralizing Anti-IFN α antibodies towards IFN α subtypes
 - Anti-IFN α and anti-KLH antibody isotyping
 - IFN β cross neutralization
 - Antibody response to influenza vaccination
- To assess correlations between immune responses, IFN gene signature and clinical responses

2.3 Investigational plan

2.3.1 Study design and randomization

This is a Phase IIb, randomized, double-blind, placebo-controlled, multicenter study assessing intramuscular (IM) administration of IFN-K against an adjuvanted placebo. Study patients are enrolled into one of two treatment groups and allocated with a 1:1 randomization ratio to receive the study product: IFN-K or placebo as outlined below:

- Group 1: IFN-K emulsified in ISA 51 VG
- Group 2: placebo emulsified in ISA 51 VG

The study consists in a main study (double-blind) followed by an Extended Follow up Period (open label).

During the main study, each patient receives two injections of study product (corresponding to 240 mcg of IFN-K or placebo) at three visits during the Induction Period (at Week 0 [Visit 2], Week 1 [Visit 3], and Week 4 [Visit 4]). Each patient is administered one injection of study product (corresponding to 120 mcg of IFN-K or placebo) during the Maintenance Period (at Week 12 [Visit 6] and Week 24 [Visit 9]).

Statistical Analysis Plan

Study Name: IFN-K-002

SAP version & date: v4, 18/Jun/2018

The main study comprises a total of 12 visits occurring over a period of 40 weeks. The study is divided into four periods: a 4-week Screening Period that is performed to determine eligibility of the patients for randomization into the study, a 12-week Induction Period, a 12-week Maintenance Period and a 12-week Follow-up Period.

The Extended Follow up Period applies to all patients who have completed the main study. Then, when the results of the main study are available, only patients who have received IFN-K will continue the Extended Follow-up Period for up to 60 months (240 weeks) after Visit 12 (Week 36).

Treatment allocation at each site is performed using central randomization via an Interactive Web Response System (IWRS). The randomization algorithm was developed using a stochastic minimization with a minimization assignment probability parameter of 0.80. Randomization is minimized on:

- Ethnic Origin: Black, Asian, Caucasian/Hispanic, other
- Age: 18-40 or 41-65 years old
- Presence or absence of renal BILAG at screening
- With or without CS treatment at randomization
- With or without HCQ treatment at randomization
- With or without MMF treatment at randomization

At the time of randomization, the IWRS assigns the patient to a treatment arm and provides the number of the treatment kit for the first injection. The actual kit number administered to the patient is recorded in the eCRF.

2.3.2 Determination of sample size

The primary objective of this study is to evaluate the neutralization of the IFN gene signature following treatment with IFN-K, as measured by the change from baseline of the expression of IFN-induced genes **and** to evaluate the efficacy of treatment with IFN-K using the British Isles Lupus Assessment Group (BILAG)-based Composite Lupus Assessment (BICLA) response criteria. The following assumptions were made for the sample size calculation:

- The error probability for a 2-sided t-test should not exceed 5%;
- The power should be 80% or higher;
- The change of the expression of IFN-induced genes in patients treated with IFN-K is assumed to be -22.6% (data from study IFN-K-001, Lauwers et al., 2013);
- The change of the expression of IFN-induced genes in patients treated with placebo is assumed to be 10% (data from study IFN-K-001, Lauwers et al., 2013);
- The common standard deviation of the change is 68 (data from study IFN-K-001, Lauwers et al., 2013).

The assumptions for the change in expression of IFN gene signature and the standard deviation are based on the original data of study IFN-K-001 as presented in Lauwers *et al.*, 2013.

With 80 evaluable patients per group i.e. a total of 160 evaluable patients, the study will have a power of 85% to detect a difference of 32.6% in the expression of IFN-induced genes in patients treated with IFN-K compared to patients treated with placebo, assuming that the common standard deviation is 68% and using

Statistical Analysis Plan

Study Name: IFN-K-002

SAP version & date: v4, 18/Jun/2018

a two group t-test with a 0.050 two-sided significance level. Assuming a rate of 10% drop-out patients, 178 patients should be enrolled in order to have 160 evaluable patients at Week 36 (80 evaluable patients in each treatment arm=90% of the enrolled patients).

Assuming a BICLA response of 20.6% in the placebo group and 40.6% in IFN-K treated patients (i.e. an absolute difference of 20%) with 80 evaluable patients per group, there will be a 73% power to detect a difference of 20% in the BICLA response criterion.

The sample size needed to ensure a 80% power to the comparison of BICLA response rates between IFN-K and placebo for different response rates in the placebo arm and varying between groups differences are presented in Figure 2 of the protocol. 97 evaluable patients per group would be needed for a power of 80% to detect a difference of 20% with a placebo response rate of 20.6%.

Statistical Analysis Plan

Study Name: IFN-K-002

SAP version & date: v4, 18/Jun/2018

2.3.3 Study assessments and study plan

Visit	1	2	3	4	5	6	7	8	9	10	11	12	FU1*	FU2*
Week	max -4	0	1	4	8	12	16	20	24	28	32	36	60	84
		Dose 1 240 mcg	Dose 2 240 mcg	Dose 3 240 mcg		Dose 4 120 mcg			Dose 5 120 mcg				108	132
Informed consent	●												156	180
Demographic data	●												204	228
SLE-specific and general medical history including alcohol, drug, and tobacco use. For US patient ONLY, screening for malignancy within the previous 12 months according to ACS	●												252	276
Complete physical examination ¹	●	●	●	●	●	●	●	●	●	●	●	●	●	●
Gynecological examination ²	●												●	
ECG (12-lead)	●	●				●			●			●		
Chest X-ray		●										●		

Confidential

Statistical Analysis Plan

Study Name: IFN-K-002

SAP version & date: v4, 18/Jun/2018

Visit	1	2	3	4	5	6	7	8	9	10	11	12	FU1*	FU2*
Week	max -4	0	1	4	8	12	16	20	24	28	32	36	60 108 156 204 252	84 132 180 228 276
		Dose 1 240 mcg	Dose 2 240 mcg	Dose 3 240 mcg		Dose 4 120 mcg			Dose 5 120 mcg					
Vital signs ³	•	•	•	•	•	•	•	•	•	•	•	•	•	•
Evaluation of eligibility	•	•												
Randomization		•												
Check contraindications		•	•	•		•			•					
Administration of study product ⁴		•	•	•		•			•					
Hematology, coagulation and biochemistry (complete) ⁵	•	•		•		•			•			•		
Hematology, coagulation and biochemistry (disease-oriented) ⁵					•		•	•		•	•		•	•
Lymphocytes count (Total, CD4+, CD8+)		•				•			•			•	•	•
Viral serology ⁶	•													
Anti-IFN α binding antibodies		•		•	•	•	•		•	•	•	•	•	•

Confidential

Statistical Analysis Plan

Study Name: IFN-K-002

SAP version & date: v4, 18/Jun/2018

Visit	1	2	3	4	5	6	7	8	9	10	11	12	FU1*	FU2*
Week	max -4	0	1	4	8	12	16	20	24	28	32	36	60 108 204 252	84 132 180 228 276
		Dose 1 240 mcg	Dose 2 240 mcg	Dose 3 240 mcg		Dose 4 120 mcg			Dose 5 120 mcg					
Anti-IFN α neutralizing antibodies		●				●	●		●	●	●	●	●	●
Neutralizing Anti-IFN α antibodies towards IFN α subtypes		●				●	●		●	●	●	●		● ¹¹
Anti-IFN α and anti-KLH antibody isotyping		●				●			●			●		
IFN β cross neutralization		●				●			●			●		
Anti-KLH binding antibodies		●				●	●		●	●	●	●	●	●
Anti-dsDNA antibodies	●	●				●			●		●	●	●	●
ANA	●	●				●			●		●	●	●	●
Other auto-antibodies (anti-Sm, anti-RNP, anti-SSA/Ro, anti-SSB/La, anti-cardiolipin and anti- β_2 -glycoprotein I antibodies)		●				●			●		●			● ¹¹
Inflammatory markers (C3, C4, CH50)	●	●		●	●	●	●		●	●	●	●	●	●

Confidential

Statistical Analysis Plan

Study Name: IFN-K-002

SAP version & date: v4, 18/Jun/2018

Visit	1	2	3	4	5	6	7	8	9	10	11	12	FU1*	FU2*
Week	max -4	0	1	4	8	12	16	20	24	28	32	36	60 108 156 204 252	84 132 180 228 276
		Dose 1 240 mcg	Dose 2 240 mcg	Dose 3 240 mcg		Dose 4 120 mcg			Dose 5 120 mcg					
IFN gene signature (RT-qPCR)	•													•
IFN gene signature (Affymetrix)		•				•			•		•			• ¹¹
Serum pregnancy test ⁷	•													
Urine pregnancy test ⁷		•	•	•	•	•	•	•	•	•	•	•		•
Urine analysis including dipstick and microscopic examination	•	•		•	•	•	•	•	•	•	•	•		•
SLEDAI-2K	•	•				•			•		•	•	•	•
PGA	•	•				•			•		•	•	•	•
BILAG-2004 index	•	•		•	•	•	•	•	•	•	•	•		
SELENA-SLEDAI flare index		•							•		•	•	•	•
SLICC/ACR DI		•									•			

Confidential

Statistical Analysis Plan

Study Name: IFN-K-002

SAP version & date: v4, 18/Jun/2018

Visit	1	2	3	4	5	6	7	8	9	10	11	12	FU1*	FU2*
Week	max -4	0	1	4	8	12	16	20	24	28	32	36	60 108 204 252	84 132 180 228 276
		Dose 1 240 mcg	Dose 2 240 mcg	Dose 3 240 mcg		Dose 4 120 mcg			Dose 5 120 mcg					
28-Tender and Swollen joint counts		●				●			●			●		
Joint Pain VAS		●				●			●			●	●	●
CLASI		●				●			●			●		
SF-36 survey score		●				●			●			●	●	●
FACIT fatigue score		●				●			●			●	●	●
Record prior medication and vaccination	●													
Record concomitant medication		●	●	●	●	●	●	●	●	●	●	●	●	●
Influenza vaccination	As needed from Visit 5 at each influenza season except within 7 days before or after study product administration													
Anti-Influenza antibody response	Should be performed 28 days +/-7 days after each flu vaccination													
Record solicited injection site reactions 1 hour post study product administration ⁸		●	●	●		●			●					

Confidential

Statistical Analysis Plan

Study Name: IFN-K-002

SAP version & date: v4, 18/Jun/2018

Visit	1	2	3	4	5	6	7	8	9	10	11	12	FU1*	FU2*
Week	max -4	0	1	4	8	12	16	20	24	28	32	36	60 108 204 252	84 132 180 228 276
		Dose 1 240 mcg	Dose 2 240 mcg	Dose 3 240 mcg		Dose 4 120 mcg			Dose 5 120 mcg					
Record solicited systemic AEs 1 hour post study product administration ⁹		•	•	•		•			•					
Provision of diary card for daily recording of solicited AEs by patients ¹⁰		•	•	•		•			•					
Return, checking and transcription of diary card			•	•	•		•			•				
Record all AEs		•	•	•	•	•	•	•	•	•	•	•		

ACR = American College of Rheumatology; ACS = American Cancer Society; AE = Adverse event; ANA = Anti-nuclear antibodies; BILAG = British Isles lupus assessment group; CLAS = Cutaneous lupus erythematosus disease area and severity index; CRP = C-reactive protein; CS = corticosteroids; DNA = Deoxyribonucleic acid; ECG = Electrocardiogram; FACIT = Functional assessment of chronic illness therapy; IFN = Interferon; KLH = Keyhole limpet hemocyanin; PGA = Physician's global assessment; RT qPCR = Reverse transcription quantitative polymerase chain reaction; SELENA = Safety of estrogen in lupus erythematosus national assessment; SF-36 = Short form-36 questionnaire; SLE = Systemic lupus erythematosus; SLEDAI = SLE disease activity index; SLICC = System Lupus International Collaborating Clinics; VAS = Visual analog scale.

¹ Including body temperature, weight and height; height being measured only during screening.

² Including examination of the cervix, and detection of high risk HPV (by RT qPCR) on PAP smear; unless performed and documented 3 months prior to the first planned study product administration.

³ Vital signs include brachial pulse and blood pressure. They will be performed after patient has been in a supine position for 3 minutes. At Visits 2, 3, 4, 6 and 9, vital signs will be performed prior to and 1 hour post study product administration.

Confidential

Statistical Analysis Plan

Study Name: IFN-K-002

SAP version & date: v4, 18/Jun/2018

⁴ 240 mcg study product administration at Visit 2, 3 and 4. 120 mcg study product administration at Visit 6 and 9.

⁵ Blood samples are to be taken prior to administration of the study product, when applicable.

- Complete means Hemoglobin, complete blood cell count and differential (Red Blood Cells, White Blood Cells, Neutrophil, Lymphocyte, Platelet), INR, PT, PTT, fibrinogen, serum Urea, serum Albumine, serum creatinine level, serum Total protein, Creatinine clearance GFR, Serum Alanine Aminotransferase, Aspartate Aminotransferase, Alkaline Phosphatase, Coombs test, Circulating Anti-Coagulant, Creatine Phospho Kinase. CD19 counts will be performed at Visit 2.
- Disease oriented means Hemoglobin, complete blood cell count and differential (Red Blood Cells, White Blood Cells, Neutrophil, Lymphocyte, Platelet), INR, PT, PTT, fibrinogen, serum Urea, serum Albumine, serum creatinine level, serum Total protein, Creatinine clearance GFR, Coombs test, Circulating Anti-Coagulant, Creatine Phospho Kinase

⁶ Screening virology testing at Visit 1: HBV [HBsAg], HCV, HIV, CMV, VZV, EBV, HTLV 1-2, and HSV-1, HSV-2.

⁷ Serum and urine pregnancy tests for female patients of childbearing potential only.

⁸ Solicited injection site reactions will be recorded by study staff 1 hour post study product administration by asking the patient about his/her perception of pain and itching sensation and via visual assessment of redness, swelling and induration.

⁹ Solicited systemic AE will be recorded by study staff 1 hour post study product administration, in particular headache, fatigue, myalgia, nausea, and fever.

¹⁰ Daily recording by patients of the presence or absence and severity of solicited local and systemic reactions on the day of the injection and the six subsequent days (i.e., 7 days in total)

¹¹ At extended follow-up, to be tested at patient's last visit only.

* The extended follow-up period will last for 5 years (i.e. 60 additional months, 69 months since 1st injection), with one visit every 6 months.

Statistical Analysis Plan

Study Name: IFN-K-002

SAP version & date: v4, 18/Jun/2018

3 Analysis datasets

3.1 Reasons for excluding patients from analysis datasets

All deviations will be reviewed and adjudicated as either major or minor during the blind data review meeting before database lock and code break.

3.1.1 Major protocol deviations

Major protocol deviations leading to patient's exclusion from the Per Protocol population are defined as deviations liable to prevent or change the interpretation of the results of the primary efficacy analysis of the study. The following deviations may be considered as major (the list is not exhaustive and maybe modified at the time of the blind review):

- Non-compliance with the inclusion or non-inclusion criteria
- non-compliance with the randomization procedure
- non-compliance with study treatment
- intake of forbidden medication

3.1.2 Minor protocol deviations

Deviations not identified as 'major' will be considered to be minor.

3.2 Study treatment discontinuations - Study discontinuations

3.2.1 Study treatment discontinuations

If any of these AEs or conditions occur during the study, the patient must not receive additional doses of study product but should be encouraged to continue other study procedures until at least Week 36. The patient must be followed until resolution of the event or condition:

- Bronchospasm or anaphylactic reaction following the administration of study product.
- Any confirmed or suspected immunosuppressive or immunodeficient condition.
- Medications leading to discontinuation of study product (list in Protocol Section 10.7.2).

3.2.2 Study discontinuations

A patient is considered to have completed the main study when he or she completes the final assessment visit (Visit 12 at Week 36). A study termination eCRF page should be completed for every patient who received study product, whether or not the patient completed the study (applicable for both main study and Extended Follow up study). Therefore, study termination page will not be available for patients who achieved visit 12 (week 36) and entered Extended Follow-up period during the double blind period.

Statistical Analysis Plan

Study Name: IFN-K-002

SAP version & date: v4, 18/Jun/2018

If a patient is discontinued prematurely at any time after entering the study, the Investigator makes every effort to see the patient and complete an early termination visit.

The reason for any early discontinuation should be indicated on the termination page. The primary reason for a patient withdrawing prematurely should be selected from the following standard categories of early termination:

- Inclusion not met / Exclusion criteria met
- Adverse event
- Protocol deviation
- Medical decision: Clinical or laboratory events occurred that in the medical judgment of the Investigator for the best interest of the patient are grounds for discontinuation. This includes serious and non-serious AEs regardless of relation to study medication.
- Death: The patient died.
- Pregnancy: The patient became pregnant.
- Withdrawal of Consent: The patient desired to withdraw from further participation in the study in the absence of an Investigator-determined medical need to withdraw. If the patient gave a reason for withdrawal, it should be recorded in the eCRF.
- Lost to Follow-Up: The patient stopped coming for visits, and study personnel were unable to contact the patient.
- Other: The patient was terminated for a reason other than those listed above, such as termination of the study by the Sponsor.

3.3 Analysis dataset definitions

3.3.1 Full Analysis Set (FAS)

The primary efficacy analysis population is the Full Analysis Set (FAS). It will include all randomized patients who received at least one dose of the study product (IFN-K or placebo). This population will be analyzed according to the result of the random treatment assignment.

3.3.2 Per-protocol (PP) dataset

The PP population will be a subset of the FAS including all randomized patients having received at least one dose of study product (IFN-K or placebo), and who complied with the procedures defined in the protocol (*i.e.*, who did not have major protocol deviations that could impact the primary endpoint analysis).

In addition, patients with at least one of the following cases will be excluded from the PP population:

- missing IFN gene signature at baseline
- missing IFN gene signature at week 24 and week 36
- missing BICLA at week 36, *i.e.*:
 - all missing BILAG at baseline
 - or missing BILAG at week 36 corresponding to a BILAG A or B at baseline
 - or all missing BILAG at week 36

Statistical Analysis Plan

Study Name: IFN-K-002

SAP version & date: v4, 18/Jun/2018

- or missing SLEDAI-2K at baseline
- or missing SLEDAI-2K at week 36
- or missing PGA on VAS 100 mm at baseline
- or missing PGA on VAS 100 mm at week 36
- less than 4 doses of study product received (out of 5)

This will also be the population used for the immunogenicity, autoantibodies and biomarkers analyses.

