Taking into account, that the number of patients will be considerable higher in this trial than in the study IFN-K-001, there is a high probability of a smaller standard deviation that could compensate for a possible smaller difference in mean changes. Therefore the sample size calculation gives a realistic estimate of the patients required for analysis to show a significant difference between active treatment and placebo.

Figure 1: Sample-size for different values of between group differences (expression of IFN-induced genes)

[figure not shown]
Assuming common SD=68 and a 0.05 two-sided type-one error rate

Assuming a BICLA response of 20.6% in the placebo group and 40.6% in IFN-K treated patients (i.e. an absolute difference of 20%) with 80 evaluable patients per group, there will be a 73% power to detect a difference of 20% in the BICLA response criterion.

The sample size needed to ensure a 80% power to the comparison of BICLA response rates between IFN-K and placebo for different response rates in the placebo arm and varying between

groups differences are presented in Figure 2. 97 evaluable patients per group would be needed for a power of 80% to detect a difference of 20% with a placebo response rate of 20.6%.

Figure 2: Sample-size for different values of between group differences (BICLA Response rate)

Assuming a power of 80% and a 0.05 two-sided type-one error rate

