4.1 Efficacy endpoints

4.1.1 Primary efficacy endpoint(s)

Two co-primary endpoints are evaluated in the trial:

- Change from baseline in the expression of IFN-induced genes at Week 36.
- Response to treatment with IFN-K as measured by the British Isles Lupus Assessment Group (BILAG)-based Composite Lupus Assessment (BICLA) response criteria at Week 36:
 - All BILAG A scores at baseline improve to B/C/D and all BILAG B scores improve to C/D at Week 36
and
○ No BILAG worsening in other body systems: no new BILAG A or ≥ 2 new BILAG B scores at Week 36
and
○ No worsening in SLEDAI-2K total score at Week 36 compared with baseline
and
○ No deterioration in PGA (< 10% worsening) on VAS 100 mm at Week 36 compared with baseline
and
○ No addition or increased dose level of anti-malarial drugs or immunosuppressive drugs or corticosteroids between Week 24 and Week 36 (this criterion will be identified by medical review)

Statistical Analysis Plan

Study Name: IFN-K-002

SAP version & date: v4, 18/Jun/2018

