5.3.2 Handling of Dropouts or Missing Data

Missing data in efficacy analysis:

For the primary endpoint – IFN gene signature – the last available value either at Visit 9 or 12 will be used for the ANCOVA model.

Missing items in questionnaires:

- SLEDAI-2K and SELENA SLEDAI:
 - At visit 6, 9 and 12 (SLEDAI-2K) or at visit 9 and 12 (SELENA-SLEDAI flare index) respectively, for descriptors “Urinary casts, Hematuria, Proteinuria, Pyuria, Low complement, Increased DNA binding, Thrombocytopenia, Leukopenia”, if value “Not done” is recorded because of no urinary/lab results available, corresponding descriptor from previous visit will be used
 - Other missing data should be considered as not present (protocol rule: items should be recorded if the descriptor is present at the time of the visit or in the preceding 10 days)
- CLASI: missing data will not be replaced. The score will be considered as missing.
- SF-36: scores for each scale are calculated for respondents completing 50% or more of the items within a scale. Among these respondents, the value for any missing item is imputed as the mean value for non-missing items (John E. Ware)
- FACIT fatigue: if there are missing items, subscale scores can be prorated. This is done by multiplying the sum of the subscale by the number of items in the subscale, then dividing by the number of items actually answered. When there are missing data, prorating by subscale in this way is acceptable as long as more than 50% of the items were answered (e.g., a minimum of 4 of 7 items, 4 of 6 items, etc). (Facit Administration and Scoring Guidelines)
- BILAG: For renal BILAG change in renal function over the last four weeks: if previous renal function is not known it will be assumed to be normal and urinalysis will be given values of 0, serum creatinine will be given a value of 100 µmol/L and creatinine clearance (GFR) will be given a value of 100 mL/min. The results entered at the first assessment will be carried forward unless replaced by new values and they should be overwritten if no longer applicable (DA Isenberg). For other cases, score is calculated with the available data.

Statistical Analysis Plan

Study Name: IFN-K-002

SAP version & date: v4, 18/Jun/2018

Missing or incomplete dates:

For calculation / sorting / assignation based on dates (e.g., treatment emergent AEs, concomitant medications...), the following rules will apply:

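### The SAP's definition of a missing Week 36 BICLA removes patients whose non-response is already established by another component

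*SAP*

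**What the plan says.** SAP 4.1.1 defines BICLA response at Week 36 by five criteria joined by *and*: improvement of every BILAG system that was A or B at baseline, no BILAG worsening elsewhere, no SLEDAI-2K worsening, no PGA deterioration, and no added or increased background drug between Weeks 24 and 36.

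SAP 3.3.2 excludes patients with missing BICLA from the PP set and spells out what missing means. The conditions are joined by *or*. They include "or missing PGA on VAS 100 mm at week 36", the same condition for SLEDAI-2K, all BILAG grades absent, and "or missing BILAG at week 36 corresponding to a BILAG A or B at baseline". The list does not mention the drug criterion and does not ask whether another criterion has already failed.

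The PP set is used to:

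- repeat the primary analysis (SAP 5.2.4.2) and judge its robustness (SAP 5.3.6);
- analyse SRI-4 a second time (SAP 5.2.4.3.1);
- describe biological parameters in BICLA responders and non-responders (SAP 5.2.4.5.13).

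The primary BICLA analysis is a logistic regression on the FAS (SAP 5.2.4.1). That section also labels an observed difference of 10% as marginal and 15% as important, regardless of statistical significance. SAP 5.3.2 gives no rule for a missing BICLA in the FAS and states that nothing beyond the listed cases is imputed. SAP 5.1.1 bases percentages on available values.

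**The concern.** When all criteria must hold, an incomplete record is of one of two kinds. If every observed component passes, the outcome is unknown. If any observed component fails, the outcome is known to be non-response whatever the absent value would have been. SAP 3.3.2 puts both kinds under one label and removes both.

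The information discarded is one-sided, because only non-responders can be identified from a partial record. Removing them raises the response rate of any arm in which it happens. It also stretches a real difference between arms, and it can create or mask a difference if it happens more often in one arm. The analysis meant to test the robustness of the primary result would then differ from it partly by construction.

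**Working it through.** **Inputs.** From Protocol 13.1: BICLA response of 20.6% on placebo and 40.6% on IFN-K, 80 evaluable of 89 enrolled per arm (10% drop-out), stated power 73%. From SAP 5.2.4.1: markers of 10 and 15 points. The share of patients with an observed failure and an absent component is given nowhere, so every f below is an assumption.

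**1. The plan's own figure.** The protocol states that "there will be a 73% power to detect a difference of 20% in the BICLA response criterion". With d = 0.200, mean rate 0.306 and n = 80 per arm, two-sided 5%:

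- Uncorrected: power = Φ[(d√n − 1.96√(2 × 0.306 × 0.694)) / √(0.206 × 0.794 + 0.406 × 0.594)] = Φ[(1.789 − 1.277)/0.636] = 78.9%.
- Continuity-corrected: n is replaced by 80 × (1 − 1/(80 × 0.200))² = 70.3, giving 73.5%.
- Fisher's exact test: 74.1%.

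The stated 73% is reproduced by a corrected or exact test.

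**2. A patient followed through the rules.** Week 36: one new BILAG A, SLEDAI-2K recorded, PGA not recorded. Under SAP 4.1.1 the new A fails the second criterion, so no PGA value could make this patient a responder. Under SAP 3.3.2 the absent PGA makes BICLA missing and the patient leaves the PP set.

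**3. Effect on a response rate.** If a share f of an arm is removed and all of them are non-responders, the responders are unchanged and the denominator shrinks. The observed rate is p/(1 − f). With the same f in both arms, the difference is also divided by 1 − f.

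| f, both arms (assumed) | True 9.0 points reads as | True 13.5 points reads as |
|---|---|---|
| 2% | 9.0/0.98 = 9.2 | 13.5/0.98 = 13.8 |
| 5% | 9.0/0.95 = 9.5 | 13.5/0.95 = 14.2 |
| 10% | 9.0/0.90 = 10.0 | 13.5/0.90 = 15.0 |

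At f = 10% both SAP markers are reached by smaller true differences. That row is an upper case: it equals the whole planned drop-out.

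**4. Unequal removal with no true effect.**

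- Rate 20.6% in both arms, 5% removed on placebo and 15% on IFN-K: 0.206/0.85 − 0.206/0.95 = 24.2% − 21.7%, or +2.6 points before rounding the rates. The reverse split gives −2.6.
- Rate 30.6% in both arms, 2% removed in one and 8% in the other: 0.306/0.92 − 0.306/0.98 = 33.3% − 31.2% = 2.0 points towards the arm that loses more.

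**5. Counting known failures under the planning assumptions.** Take the planned rates as those of the 80 evaluable patients and let a share of the 9 others per arm (89 − 80) be known failures.

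| Share of the 9 that are known failures (assumed) | Placebo | IFN-K | Difference | Power (Fisher) |
|---|---|---|---|---|
| 0% | 20.6% | 40.6% | 20.0 | 74% |
| 50% (80/84.5 of each rate) | 19.5% | 38.4% | 18.9 | 73% |
| 100% (80/89 of each rate) | 18.5% | 36.5% | 18.0 | 72% |

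The rates fall slightly and power hardly moves.

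**The case against.** **The removal is written only for a supplementary set.** This stands. The 10- and 15-point markers belong to the primary analysis, which is on the FAS. That the same patients leave the FAS regression is inferred from there being no other definition, no further imputation and percentages based on available values. A programmer could code an observed failure as non-response in the FAS without contradicting the SAP.

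**Partial records may be few.** PGA, SLEDAI-2K and BILAG are all due at the same Week 36 visit, so an absent PGA will often mean an absent visit. A steroid increase after Week 24 may already be a major deviation that leads to PP exclusion (Protocol Table 4, SAP 3.1.1). This limits the number affected in the PP set. It does not cover the patient in step 2, and a drug increase between Weeks 24 and 36 can be known without a Week 36 visit.

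**Inflation in both arms does not favour IFN-K.** Correct when removal is equal and there is no true effect. It matters when there is a real difference to stretch, or when removal is unequal, and then the sign can go either way.

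**A stronger reading that the documents do not support.** A reader might infer that all the SAP's rules for incomplete components lean towards response, by treating ungraded BILAG systems and unscored SLEDAI items as inactive.

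- For SLEDAI, "Other missing data should be considered as not present" follows the instrument's instruction to record an item when it is present (Protocol Appendix 2). Eight urine and laboratory descriptors, 22 of 105 points, can instead be carried forward from the previous visit. A blank at baseline lowers the baseline score and makes worsening more likely, so the direction is not uniform.
- For BILAG, an ungraded system that was A or B at baseline makes BICLA missing. For other systems, the idea that they pass the criterion "No BILAG worsening in other body systems" unchecked comes only from combining that list with "For other cases, score is calculated with the available data", a sentence placed under missing questionnaire items.

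**Conclusion.** The concern holds in a limited form. As written, SAP 3.3.2 labels certain non-responders as missing and excludes them from the PP set. This follows from the text and needs no assumption. Removal from the primary FAS analysis is probable but inferred.

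The size cannot be fixed from the documents. If 2% to 10% of each arm were affected, a real difference would be overstated by a factor of 1.02 to 1.11 (1/0.98 to 1/0.90). Unequal removal in the cases shown moves the difference by 2.0 to 2.6 points in either direction. If the FAS counts these patients as non-responders, the effect is confined to PP results, which would then look somewhat better than the FAS for a reason unrelated to protocol adherence. If the FAS drops them, the two analyses share the same error and their agreement is less reassuring than it seems. No systematic advantage for IFN-K is shown.

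**What to change.** In SAP 3.3.2 and 4.1.1, for both the FAS and the PP set, state that BICLA is non-response as soon as any observed component fails, including the drug criterion between Weeks 24 and 36. It is missing only when every observed component passes and at least one is absent. Limit the missing-BICLA exclusion from the PP set to that second case; the other PP exclusions can stay as they are.

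Carrying Week 28 or 32 BILAG grades, or earlier clinical SLEDAI items, into Week 36 should not be part of this change. BILAG covers the preceding 4 weeks and SLEDAI-2K the preceding 10 days, so such values come from outside the assessment window. They could serve at most as a sensitivity analysis.

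The cost is a sentence or two in each section and a few lines of derivation code, with no new data. Observed response rates may be slightly lower.
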